#### 7.5.6.2 Biomarker Analysis – ctDNA

Blood samples will be collected during screening, before dosing beginning on Day 1 of Cycles 1, 2, 3, and at specified subsequent cycles, at treatment discontinuation, and through the 100-day Follow-up Visit, as scheduled in [Table 9](#). Sample collection details will be provided in the Laboratory Manual.

These samples will be used for ctDNA profiling to assess alterations in genes that may be associated with response and resistance to the combination of rucaparib and nivolumab.

#### 7.5.6.3 Biomarker Analysis - Genomic DNA from Blood

A blood sample for genomics analysis will be collected at Cycle 1 Day 1 (or next visit if not collected at Cycle 1 Day 1) from all patients for determination of germline status of mutations identified using NGS testing. Results of actionable alterations may be made available to the investigator, subject to patients consent. Sample collection details will be provided in the Laboratory Manual.

#### 7.5.6.4 Other Peripheral Blood Biomarker Analyses

Peripheral blood samples will also be collected at selected time points on-treatment (C1D1, C2D1, C5D1, C7D1, C9D1), at the time of progression, and safety follow-ups for biomarker analyses that may predict sensitivity to nivolumab, including flow cytometry immunophenotyping, neo-epitope DNA sequencing, and serum cytokine/chemokine profiling.

A schedule of blood biomarker analysis is provided in [Table 8](#). Sample collection and processing details will be provided in the Laboratory Manual.

#### 7.5.6.5 Additional Research

The patient will have the option to provide additional consent to allow the sponsor to retain residual samples for future unspecified research.

## 8 ADVERSE EVENT MANAGEMENT

### 8.1 Definition of an Adverse Event

An AE is defined as any untoward medical occurrence in a patient administered a medicinal product that does not necessarily have a causal relationship with this treatment. An AE can, therefore, be any unfavorable and unintended sign (including an abnormal laboratory finding), symptom, or disease temporally associated with the use of an investigational product, whether or not related to the investigational medicinal product. This includes an exacerbation of pre-existing conditions or events, intercurrent illnesses, drug interaction, or the significant worsening of the indication under investigation that is not recorded elsewhere on the eCRF under specific efficacy assessments. Anticipated fluctuations of pre-existing conditions, including the disease under study, that do not represent a clinically significant exacerbation or worsening are not considered AEs.

It is the responsibility of the investigator to document all AEs that occur during the study. AEs should be elicited by asking the patient a non-leading question (eg, “Have you experienced any new or changed symptoms since we last asked/since your last visit?”). The existence of an AE may be concluded from a spontaneous report of the patient; from the physical examination; or from special tests such as the ECG, laboratory assessments, or other study-specified procedure (source of AE). Symptoms reported spontaneously by the patient during the physical examination would also qualify as an AE (and hence documented on the AE eCRF).

### 8.2 Definition of a Serious Adverse Event

An SAE is any untoward medical occurrence that occurs at any dose (or, occurs after informed consent is given and prior to dosing if the SAE is related to a study procedure) that:

- Results in death. Any event resulting in death during the reporting period (from date of first dose of study drug through 28 days after last dose of oral drug and 100 days after the last dose of IV study drug, whichever occurs later) must be treated as an SAE and reported as such. An event related to a study procedure that occurs after informed consent, but prior to dosing that results in death must also be reported as an SAE.
- Is life-threatening (patient is at immediate risk of death from the event as it occurred)
- Requires in-patient hospitalization (formal admission to a hospital for medical reasons) or prolongation of existing hospitalization
- Results in persistent or significant disability/ incapacity
- Results in a congenital anomaly or birth defect
- Important medical events that may not result in death, are not life-threatening, or do not require hospitalization may be considered SAEs when, based on appropriate medical judgment, they may jeopardize the patient and may require medical or surgical intervention to prevent one of the outcomes listed in this definition. Examples of such events include allergic bronchospasm requiring intensive treatment in an emergency room or at home or the development of drug dependency or drug abuse.

### 8.3 Definition of an Adverse Events of Special Interest

AESIs (serious or nonserious) are defined as AEs of scientific and medical concern specific to the sponsor's product or program, for which ongoing monitoring and rapid communication by the investigator to the sponsor can be appropriate. Such an event might warrant further investigation in order to characterize and understand it. Depending on the nature of the event, rapid communication by the study sponsor to other parties (eg, regulators) might also be warranted.

Details on the sponsor's currently agreed list of AESIs for rucaparib can be found in the current rucaparib IB. These AESIs are to be reported to the sponsor **within 24 hours** (see [Section 8.10](#) for reporting instructions).

### 8.4 Immune-mediated Adverse Events

Immune-mediated AEs (IMAEs) are AEs consistent with an immune-mediated mechanism or immune-mediated component for which non-inflammatory etiologies (eg, infection or tumor progression) have been ruled out. IMAEs can include events with an alternate etiology which were exacerbated by the induction of autoimmunity. Information supporting the assessment will be collected on the patient's eCRF.

Details on IMAEs can be found in the current nivolumab IB.

### 8.5 Events or Outcomes Not Qualifying as Serious Adverse Events

The following are not considered SAEs and therefore do not need to be reported as such:

- Pre-planned or elective hospitalization including social and/ or convenience situations (eg, respite care)
- Hospital visits of less than 24 hours duration (eg, patient presents to the emergency room, but is not admitted to a ward)
- Overdose of either study drug or concomitant medication unless associated with an SAE. However, the event should still be captured as a nonserious AE on the appropriate eCRF page
- Events of progression of the patient's underlying cancer as well as events clearly related to progression of the patient's cancer (signs and symptoms of progression) should not be reported as an AE or a serious adverse event.
- Events that meet the SAE criteria (as outlined in [Section 8.2](#)) and occur after informed consent but before the first dose of study drug, which are considered unrelated to screening procedures.

## 8.6 Clinical Laboratory Assessments as Adverse Events and Serious Adverse Events

It is the responsibility of the investigator to assess the clinical significance of all abnormal values as defined by the list of reference ranges from the local laboratory. In some cases, significant changes in laboratory values within the normal range will require similar judgment.

An abnormal laboratory value that is not already associated with an AE is to be recorded as an AE only if any one of the following criteria is met:

- an action on the study drug is made as a result of the abnormality
- intervention for management of the abnormality is required
- at the discretion of the investigator should the abnormality be deemed clinically significant

## 8.7 Pregnancy or Drug Exposure during Pregnancy

If a patient becomes pregnant during the course of the study, study drug(s) should be held immediately.

Pregnancy is not considered to be an AE or SAE; however, all pregnancies occurring during study participation or within 6 months of last dosing must be reported to the sponsor using the Pregnancy Report Form within the same timelines as for an SAE.

All pregnancies will be followed through to outcome. Once the outcome of a pregnancy is known, the Pregnancy Outcome Report Form will be completed and reported to the sponsor.

AEs, SAEs, or AESIs that occur during pregnancy will be assessed and processed according to the AE or SAE/ AESI processes using the appropriate AE or SAE/ AESI forms.

## 8.8 Recording of Adverse Events, Serious Adverse Events, and Adverse Events of Special Interest

Events that occur after signing of informed consent but prior to initiation of study drug, unless due to a protocol-mandated procedure, will be recorded on the Medical History eCRF. Any AE that occurs after first dose of study drug through 28 days after receiving the last dose of oral study drug or 100 days after receiving the last dose of IV study drug, whichever occurs later, will be recorded on the AE eCRF. After the 28-day or 100-day reporting window after discontinuation of treatment, only SAEs assessed as related to study drug and all AESIs, irrespective of causality, need to be reported. Information on the follow-up of AEs, SAEs, and AESIs is provided in [Section 8.9](#).

In order to avoid vague, ambiguous, or colloquial expressions, the AE should be recorded in standard medical terminology rather than the patient's own words. Whenever possible, the investigator should combine signs and symptoms that constitute a single disease entity or syndrome into a final diagnosis, if appropriate. For example, fever, cough, and shortness of breath may be reported as pneumonia, if that is a reasonable diagnosis.

Each AE is to be evaluated for **causal relationship** to the investigational drug, severity, and, seriousness. The action taken, and the outcome must also be recorded.

SAEs and AESIs that occur during the study or within 28 days after receiving the last dose of oral study drug or 100 days after receiving the last dose of IV study drug, whichever is later, whether or not related to study drug, must be reported immediately (ie, **within 24 hours** of knowledge of the event or additional information for a previously reported event) to the sponsor/SAE designee. The contact information for reporting of SAEs/AESIs can be found on the SAE/ AESI Reporting Form.

#### 8.8.1 Onset date of Adverse Events

The onset date is the date that the event or the signs or symptoms related to the event started.

#### 8.8.2 Resolution date of Adverse Events

The resolution date is the date that the event or the signs / symptoms related to the event resolved or resolved with sequelae or enter the resolution date as the date when the patient has reached a new baseline if event is not expected to resolve.

#### 8.8.3 Intensity of Adverse Events

The severity of each AE will be graded using the NCI CTCAE, v5 or later grading scale.

Severity is not the same as Serious.

For AEs not covered by NCI CTCAE, the severity will be characterized as mild, moderate, severe, life-threatening, or fatal according to the following definitions:

- Mild events are usually transient and do not interfere with the patient's daily activities
- Moderate events introduce a low level of inconvenience or concern to the patient and may interfere with daily activities
- Severe events interrupt the patient's usual daily activities and hospitalization (or prolongation of hospitalization) may be required
- Life-threatening events require urgent intervention to prevent death
- Fatal events are events that lead to the patient's death

#### 8.8.4 Causal Relationship of Adverse Events to Study Drug

Medical judgment should be used to determine the cause of the AE considering all relevant factors such as, but not limited to, the underlying study indication, coexisting disease, concomitant medication, relevant history, pattern of the AE, temporal relationship to the study medication, dechallenge or rechallenge with the study drug (Table 10).

**Table 10. Causal Relationship of Adverse Events to Study Drug**

Not Related to Study Drug	
 
• An AE that is clearly due to extraneous causes (eg, concurrent disease, concomitant medications, disease under study, etc.)
 
• It does not follow a reasonable temporal sequence from administration of the study drug.
 
• It does not follow a known pattern of response to study drug
 
• It does not reappear or worsen when study drug is restarted.
 
• An alternative explanation is likely, but not clearly identifiable.
 

Related to Study Drug	
 
• An AE that is difficult to assign to alternative causes.
 
• It follows a strong or reasonable temporal sequence from administration of study drug.
 
• It could not be reasonably explained by the patient’s clinical state, concurrent disease, or other concomitant therapy administered to the patient.
 
• It follows a known response pattern to study drug
 
• It is confirmed with a positive rechallenge or supporting laboratory data.
 

## 8.9 Follow-Up of Adverse Events, Serious Adverse Events, and Adverse Events of Special Interest

All AEs (including SAEs and AESIs) occurring during the study are to be followed up in accordance with good medical practice until resolved; judged no longer clinically significant; or, if a chronic condition, until fully characterized through 28 days after the last dose of oral study drug or 100 days after the last dose of IV study drug, whichever occurs later. Any SAEs, AESIs, and treatment-related Grade 3/4 AEs must be followed until resolution or stabilization, or until lost to follow-up. After the 28- or 100-day window, treatment-related SAEs and all AESIs, irrespective of causality, need to be reported.

## 8.10 Potential Drug-Induced Liver Injury

Wherever possible, timely confirmation of initial liver-related laboratory abnormalities should occur prior to the reporting of a potential DILI event. All occurrences of potential DILIs, meeting the defined criteria, must be reported as SAEs (see [Section 8.11](#) for reporting details).

Potential drug induced liver injury is defined as:

1. ALT or AST elevation  $> 3 \times$  ULN

AND

2. Total bilirubin  $> 2 \times$  ULN, without initial findings of cholestasis (elevated serum alkaline phosphatase),

AND

3. No other immediately apparent possible causes of ALT/AST elevation and hyperbilirubinemia, including, but not limited to, viral hepatitis, pre-existing chronic or acute liver disease, or the administration of other drug(s) known to be hepatotoxic.

### **8.11 Regulatory Aspects of Serious Adverse Event and Adverse Events of Special Interest Reporting**

It is important that the investigator provide an assessment of relationship of the SAE or AESI to study treatment at the time of the initial report. For reporting SAEs/AESIs or pregnancies, use the applicable report forms. The contact information for reporting of SAEs and AESIs can be found on each of the forms.

The sponsor or its designee is responsible for submitting reports of AEs associated with the use of the drug that are both serious and unexpected to the US FDA, according to 21 Code of Federal Regulations (CFR) 312.32; to the Japanese Pharmaceuticals and Medical Devices Agency (PMDA); to the European regulatory authorities according to the European Commission Clinical Trials Directive (2001/20/EC); and to other applicable regulatory authorities, according to national law and/or local regulations. All investigators participating in ongoing clinical studies with the study medication will receive copies of these reports for prompt submission to their IRB or IEC. In accordance with the European Commission Clinical Trials Directive (2001/20/EC), the sponsor or its designee will notify the relevant ethics committees in concerned member states of applicable suspected unexpected serious adverse reactions (SUSARs) as individual notifications or through periodic line listings.

The sponsor or its designee will submit all safety updates and periodic reports to the regulatory authorities as required by applicable regulatory requirements.

### **8.12 Data Monitoring Committee**

A study DMC will be established and be comprised of the coordinating investigator and sponsor representatives. The DMC composition, responsibilities, and procedures for this study will be documented in the DMC Charter, which will be endorsed by the DMC members and signed by the DMC chair prior to the first data review meeting.

The DMC will review on an ongoing basis the study progress and clinical data to ensure the study remains beneficial to patients. The DMC will review the overall safety and efficacy data of rucaparib in combination with nivolumab, and by study cohort, to determine whether the study benefit/risk remains positive during the study.

The DMC will meet after the first 10 patients (Cohort A1) have either (a) received at least one Cycle of study treatment with Rucaparib and Nivolumab, (b) discontinued study treatment or (c) died of any cause. The DMC will perform continuous safety review at least every 6 months. The DMC chairperson or sponsor may convene an unscheduled DMC meeting if there are any emergent significant safety concerns. Following data review, the DMC will recommend

continuation, revision, or termination of the study and/or continuing or suspending enrollment into the study or a particular study cohort.

## 9 PLANNED STATISTICAL METHODS

### 9.1 General Considerations

All safety analyses will be summarized for all patients who received at least 1 full or partial dose of protocol-specified treatment. Efficacy will be summarized for all treated patients according to the intent-to-treat principle. Cohorts A1 and A2 will be summarized separately for all safety and efficacy analyses.

Quantitative variables will typically be summarized using frequencies and percentages for appropriate categorizations and may also be summarized using descriptive statistics. For variables summarized with descriptive statistics, the following will be presented: N, mean, standard deviation (StD), median, minimum, and maximum. Categorical variables will be presented using frequencies and percentages.

The Kaplan-Meier methodology will be used to summarize time-to-event variables. If estimable, median (50th percentile) with the 95% confidence interval (CI) will be summarized. The number of patients with events and the number of censored patients will also be presented.

All data will be used to their maximum possible extent but without any imputations for missing data. Unless otherwise specified, baseline is defined as the last measurement on or prior to the first day of study drug administration.

All statistical analyses will be conducted with the statistical analysis software (SAS®) System, Version 9.3 or higher. Further details around the statistical analyses planned in this study will be outlined in the Statistical Analysis Plan (SAP).

### 9.2 Determination of Sample Size

Between 28 to 53 patients will be enrolled in this non-randomized 2-cohort study, which includes a 2-stage study design for Cohort A1.

- Cohorts A1 and A2 (Ovarian): Oral rucaparib + IV nivolumab
  - Cohort A1 (n = 18-43)
  - Cohort A2 (n = approximately 10)

#### 9.2.1 Cohort A1

For Cohort A1, a Simon 2-stage design to evaluate ORR by RECIST v1.1 criteria per investigator will be used. With an optimal design, a minimum of 18 patients will be enrolled and a maximum of 43 patients. After the first 18 patients have either **a**) completed 16 weeks of treatment, or **b**) discontinued treatment prior to completing, an interim analysis will be performed (ie, Stage 1). If  $\leq 2/18$  patients in Stage 1 have a confirmed objective response (CR or

PR per investigator), a DMC will evaluate the overall benefit: risk for study treatment and make a recommendation whether further enrollment should be discontinued. If  $\geq 3/18$  patients have a confirmed objective response, then enrollment will continue with additional patients in Stage 2. With 43 total patients, characteristics of the Simon 2-stage design include:

- 5% probability of accepting a minimally effective drug (ie, ORR of 10%)
- 80% probability of accepting an effective drug (ie, ORR of 25%)

### 9.2.2 Cohort A2

Cohort A2 is an exploratory cohort which will enroll approximately 10 patients classified as gBRCAmut.

## 9.3 Analysis Populations

**Safety Population:** The Safety Population will consist of all patients who received at least 1 full or partial dose of any protocol-specified treatment.

## 9.4 Patient Disposition

Patient disposition will be summarized using frequency counts and the corresponding percentages. The number of patients in each analysis population, number of patients discontinued, and the primary reason for discontinuation from treatment will be summarized.

## 9.5 Demographics and Baseline Characteristics

All demographic (eg, age, race, and ethnicity as allowed by local regulations) and baseline characteristics will be summarized for the safety population.

The following disease and baseline characteristics variables will also be summarized with frequency tabulations:

- Time since diagnosis (months): > 12 to 24, > 24
- Baseline laboratory parameters: graded based on CTCAE

Molecularly defined subgroups based on HRD and TMB and other definitions as appropriate.

- Number of prior anticancer regimens; also split out by
  - Number of prior chemotherapy regimens
  - Number of prior platinum-based regimens
- Progression-free interval following the last platinum regimen received (months); 0-6, > 6-12, > 12-24, > 24;
- Partially Sensitive: PD  $\geq 6$  to < 12 months after last dose of platinum
- Sensitive: PD  $\geq 12$  months after last dose of platinum

Descriptive statistics may also be used to summarize the continuous variables.

## 9.6 Efficacy Analyses

All primary and secondary efficacy analyses will be summarized for the Safety Population for Cohort A1. Cohort A2 has an exploratory objective for evaluation of rucaparib on the immune microenvironment (see [Section 9.6.3](#)).

### 9.6.1 Primary Efficacy Analyses

The primary efficacy endpoint of ORR is defined as a best confirmed response of CR or PR by RECIST v1.1 as assessed by the investigator. The confirmed response rate by RECIST v1.1 is defined as the proportion of patients with a confirmed CR or PR on subsequent tumor assessment at least 28 days after first response documentation. The ORR will be summarized with frequencies and proportion together with 95% CI of the proportion using Clopper-Pearson methodology.

### 9.6.2 Secondary Efficacy Analysis

#### 9.6.2.1 ORR Assessed by RECIST and GCIG CA-125 Criteria

The endpoint of ORR assessed by RECIST v1.1 or GCIG CA-125 criteria is defined as a best confirmed response of CR or PR using RECIST v 1.1 as assessed by the investigator or a confirmed response per GCIG CA-125 criteria. The endpoint of CA-125 response rate defined as at least a 50% reduction in CA-125 as assessed by GCIG criteria ([Appendix 2](#)). The response rate will be summarized with frequencies and percentages in addition to 95% CI of the proportion using Clopper-Pearson methodology. The combined ORR will be assessed as indicated in [Table 11](#).

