## 5.10 Treatment of Study Drug beyond Disease Progression

Patients will receive study drug until confirmed radiologic disease progression as assessed by investigator using RECIST v1.1 criteria, unacceptable toxicity or inability to tolerate further treatment, loss to follow-up, death, or withdrawal of consent.

If a patient receiving study drug has met criteria for confirmed radiologic disease progression by RECIST v1.1 criteria, but the patient continues to derive clinical benefit per the investigator, then continuation of treatment will be permitted. In such cases, the investigator's decision to continue treatment should be documented in the source documents and the sponsor's medical officer or designee should be informed. The patient must provide additional consent at their next scheduled study visit to continue treatment with study drug. Clinical scenarios where continuation of study drug after radiographic progression may be considered include 1) a patient for whom radiographic progression develops slowly while disease-related symptoms remain well controlled, 2) a patient who experiences progression in a site of disease that is unlikely to adversely affect prognosis (eg, enlargement of a solitary lymph node), or 3) a patient with general disease control but limited progression in sites of disease that can be managed with local therapies such as surgery or radiation. Patients continuing to receive study drug will continue to have all protocol-required assessments as described in [Section 7](#).

Continuation of treatment will be considered for a maximum cumulative duration of 24 months after initiation of oral/IV combination study treatment, or until confirmation of further progression as assessed by the investigator, whichever is sooner.

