**Table 11. RECIST and GCIG CA-125 Criteria**

RECIST Response	GCIG CA-125 Response	RECIST + GCIG CA-125 Combined
CR (requires normalization of CA-125)	CA-125 within normal range	Response
PR	Response	Response
PR	No Response	Response
SD	Response	Response
SD	No Response	No Response
PD	Response	No Response
PD	No Response	No Response

Abbreviations: CA-125 = cancer antigen 125; CR = complete response; GCIG = Gynecologic Cancer InterGroup; PD = progressive disease; PR = partial response; RECIST = Response Evaluation Criteria in Solid Tumors; SD = stable disease

The response rate will be summarized with frequencies and percentages in addition to 95% CI of the proportion using Clopper-Pearson methodology.

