### Evaluation of Best Overall Response

The best overall response is the best response recorded from the start of the treatment until disease progression/recurrence (taking as reference for PD the smallest measurements recorded since the treatment started).

Evaluation of Best Overall Response: Patients with Target (±Non-Target) Disease			
Target Lesions	Nontarget Lesions	New Lesions	Overall Response
CR	CR	No	CR
CR	Non-CR/non-PD	No	PR
CR	Not evaluated	No	PR
PR	Non-PD or not evaluated	No	PR
SD	Non-PD or not evaluated	No	SD
Not Evaluated	Non-PD	No	NE
PD	Any	Yes or No	PD
Any	PD	Yes or No	PD
Any	Any	Yes	PD

Evaluation of Best Overall Response: Patients with Non-Target Disease Only		
Nontarget Lesions	New Lesions	Overall Response
CR	No	CR
Non-CR/non-PD	No	Non-CR/non-PD a
Not all evaluated	No	NE
Unequivocal PD	Yes or No	PD
Any	Yes	PD

a 'Non-CR/non-PD' is preferred over 'stable disease' for non-target disease since SD is increasingly used as endpoint for assessment of efficacy in some studies so to assign this category when no lesions can be measured is not advised.

Patients with global deterioration of health status requiring discontinuation of treatment without objective evidence of disease progression at that time should be classified as having symptomatic deterioration. Every effort should be made to document the objective progression, even after discontinuation of treatment.

In some circumstances, it may be difficult to distinguish residual disease from normal tissue. When evaluation of CR depends on this determination, it is recommended that the residual lesion be investigated (fine needle aspiration/biopsy) prior to confirming the complete response status.

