## **Appendix 2            Modified Gynecological Cancer Intergroup (GCIG) Guidelines for Response Using CA-125**

GCIG Guidelines for Response Using CA-125 (adapted for use in this study).

GCIG CA-125 definitions are available at <http://gcig.igcs.org/CA-125.html>.

To be evaluable for response by CA-125 requires an elevated baseline value of at least 2 x ULN and at least 2 additional samples after the start of treatment.

A response to CA-125 has occurred if there is at least a 50% decrease as the result of the treatment. The pre- and post-treatment samples must satisfy the following criteria:

1. There must be at least 1 sample that is  $> 2 \times$  ULN prior to initiation of treatment
2. The second sample (post-treatment) must be  $\leq 50\%$  of the pre-treatment sample;
3. The confirmatory third sample must be  $\geq 21$  days after the second sample and  $\leq 110\%$  of the second sample;
4. Any intervening samples between samples 2 and 3 must be  $\leq 110\%$  of the previous sample unless considered to be increasing because of tumor lysis.

Patients are not evaluable by CA-125 if they have received mouse antibodies or if there has been medical or surgical interference with their peritoneum or pleura during the previous 28 days.

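### The combined RECIST/CA-125 response needs one governing rule and a date limit: its defining sentence and Table 11 disagree on progression, and a CA-125 fall after progression can be read as a response

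*Combined protocol and SAP*

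**What the plan says.** Section 9.6.2.1 gives two statements of the endpoint in one paragraph. The defining sentence joins a best confirmed RECIST CR or PR to the tumor marker by an either/or: "as assessed by the investigator or a confirmed response per GCIG CA-125 criteria". Later the paragraph says "The combined ORR will be assessed as indicated in" Table 11. That table, whose result column is "RECIST + GCIG CA-125 Combined", contains the row "PD Response No Response" and the row "SD Response Response". It carries no dates.

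The time windows of the two components are stated differently:

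- RECIST (Appendix 1): "The best overall response is the best response recorded from the start of the treatment until disease progression/recurrence".
- CA-125 (Appendix 2): "A response to CA-125 has occurred if there is at least a 50% decrease as the result of the treatment". The appendix then sets the baseline level, the size of the fall, the spacing and the confirmation. It sets no last date.

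Section 5.10 covers a patient who has met the RECIST progression criteria, "but the patient continues to derive clinical benefit per the investigator, then continuation of treatment will be permitted", and keeps all protocol-required assessments running. Section 7.5.3.2 has CA-125 drawn at the start of every cycle. Table 6 also lists it at end of treatment, at both safety follow-up visits and in long-term follow-up.

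Sections 9.6.2.3 and 9.6.2.4 (PFS and DOR) do deal with post-progression data: the first progression date is used, and only scans before subsequent anticancer treatment count.

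**The concern.** There are two gaps. First, the sentence that defines the endpoint and the table that operates it give opposite answers for one kind of patient: RECIST PD with a CA-125 response. Second, even if the table governs, it crosses two components when only one has a closing date. The protocol allows treatment and marker sampling past progression, so a CA-125 fall after progression can be observed and can enter the endpoint.

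At stake is a secondary endpoint of Cohort A1. Section 9.6.2.2 carries the same method into the HRD subgroups, where denominators are smaller and each case weighs more, and Section 9.6.3 lists the endpoint for Cohort A2. Compared with a rule that closes the CA-125 window at progression, the open window can only add responders. If the rule is settled after the data are seen, the choice is open to the criticism that the result guided it.

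**Working it through.** **1. The two rules side by side.** Each combination is scored under the defining sentence of Section 9.6.2.1 and under Table 11.

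| RECIST | CA-125 | Defining sentence | Table 11 |
|---|---|---|---|
| CR | within normal range | Response | Response |
| CR | not normalized | Response | no row |
| PR | Response | Response | Response |
| PR | No Response | Response | Response |
| SD | Response | Response | Response |
| SD | No Response | No Response | No Response |
| PD | Response | Response | No Response |
| PD | No Response | No Response | No Response |
| NE | Response | Response | no row |
| NE | No Response | No Response | no row |

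Where both rules give an answer they differ only for PD with a CA-125 response. Table 11 gives no answer for NE, nor for CR without normalization. It also has no row for the Non-CR/non-PD category of Appendix 1. That category can arise in Cohort A2, because inclusion criterion 7 requires measurable disease in Cohort A1 only.

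**2. The time order.** Take a patient with pre-treatment CA-125 above 2 × ULN, best RECIST response SD, and then RECIST progression. She continues study drug under Section 5.10. Her CA-125 then falls to 50% or less of the pre-treatment value and is confirmed at least 21 days later. Appendix 2 is met. If the RECIST column of Table 11 is best response up to progression, as Appendix 1 defines it, the entry is SD and the result is Response. If the column is read as RECIST status when the marker falls, the entry is PD and the result is No Response. The table does not say which. The defining sentence speaks of best response, so the first reading is a natural one.

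**3. Size.** The plan states no target rate or power for this endpoint, so there is no figure of its own to reproduce. The maximum size of Cohort A1 is 43 (Section 9.2.1). One patient is 1/43 = 2.3 points, two are 2/43 = 4.7 and three are 3/43 = 7.0. The documents give no frequency; 0 to 3 is an assumption.

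As an illustration, assume 14 responders under a time-ordered Table 11. Clopper-Pearson 95% intervals are:

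| Extra cases | Responders | Rate | 95% CI |
|---|---|---|---|
| 0 | 14/43 | 32.6% | 19.1 to 48.5 |
| 1 | 15/43 | 34.9% | 21.0 to 50.9 |
| 2 | 16/43 | 37.2% | 23.0 to 53.3 |
| 3 | 17/43 | 39.5% | 25.0 to 55.6 |

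The base of 14 was chosen to lie near the non-tBRCA rate by RECIST or CA-125 in Table 1: (36 + 14 + 4)/(82 + 70 + 12) = 54/164 = 32.9%. That row of Table 1 is not internally consistent: its four subgroups sum to 34 + 36 + 14 + 4 = 88, but the printed total is 91. Total minus tBRCA would give (91 − 34)/164 = 57/164 = 34.8%. The illustration does not depend on which is right.

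**4. What is not touched.** The primary endpoint (Section 9.6.1) is RECIST only. An exact search for the optimal Simon design at 10% versus 25% returns 18 then 43 patients, continuing if at least 3 of 18 respond and succeeding if at least 8 of 43 respond, with type I error 0.0480 and power 0.8003. This agrees with Section 9.2.1 and does not involve CA-125.

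**The case against.** The strongest reply is that the paragraph itself says how the combined rate is assessed, namely by Table 11. On that reading the defining sentence names the components and the table says how they combine. This largely stands. A reader might infer that the plan has two competing operative rules and that patients whose best response is PD will be counted as responders. The documents do not support going that far. What remains is a defining sentence that contradicts the table and should be reworded.

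On timing, the RECIST column of Table 11 is not labeled as best response, so a patient already in progression could be placed in the PD row. That is fair: the SD reading is available and natural, but not compelled. The sequence is also narrow. It needs SD, then progression, then continued treatment with additional consent, an elevated baseline marker, no qualifying fall before progression, and a confirmed fall afterwards measured against the pre-treatment value. It may never happen. Appendix 2 does require the fall to result from treatment. That wording bears on falls under a later therapy, but it is not a date rule and does not exclude a fall on study drug continued past progression.

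A reader might also take the rise from 34/164 (20.7%) by RECIST to 54/164 (32.9%) by RECIST or CA-125 in Table 1 as the size of the bias. It is not. It shows the ordinary contribution of CA-125 to such an endpoint, in a row that does not add up.

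Finally, Section 9.1 leaves further statistical detail to the SAP, and a window could be set there. That would settle the timing, but the conflict within Section 9.6.2.1 would still need correcting.

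**Conclusion.** The point holds as a needed clarification of a secondary endpoint. The defining sentence and Table 11 conflict on PD with a CA-125 response, and the paragraph's reference to the table largely settles which applies. The missing time limit is the more substantive gap, because it persists when Table 11 governs and because PFS and DOR in the same section do have such a limit. The possible error runs in one direction, toward a higher combined rate, at 2.3 points per patient in 43: 0 to 7.0 points for an assumed 0 to 3 patients. With 14 of 43 responders the interval is already about 29 points wide (48.5 − 19.1 = 29.4), so one case would not change the interpretation of the whole cohort.

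The documents do not show that the combined rate will be inflated, only that the rules permit it. Nothing here bears on the primary ORR, the Stage 1 rule or the sample size.

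**What to change.** In Section 9.6.2.1 and Table 11:

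1. Reword the either/or sentence so that combined response is determined by Table 11.
2. State that the RECIST column is the best confirmed RECIST response up to first progression.
3. Count a CA-125 response only if its first qualifying sample (sample 2 in Appendix 2) is dated on or before first RECIST progression, and both that sample and the confirming sample precede any subsequent anticancer treatment.
4. Add rows for NE with and without a CA-125 response, for Non-CR/non-PD in Cohort A2 with and without a CA-125 response, and for RECIST CR without CA-125 normalization. Without these rows, letting Table 11 govern would leave unassigned some patients whom the present sentence counts as responders.

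Apply the same wording to the HRD subgroup and Cohort A2 versions, and settle it before the analysis. The cost is a few sentences and a date check on data already collected. No visit, sample or treatment rule changes. The reported combined rate may be slightly lower.
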